#### 3.2 Secondary Objective(s) & Hypotheses

(1) **Objective:** To characterize freedom from distant metastasis rates following treatment with sequential pembrolizumab and radiotherapy for locally advanced NSCLC with PD-L1 expression  $\geq 50\%$ .

**Hypothesis:** We hypothesize that sequential pembrolizumab and radiotherapy for locally advanced NSCLC with PD-L1 expression  $\geq 50\%$  prolongs freedom from distant metastasis compared to historical outcomes.

(2) **Objective:** To characterize freedom from intrathoracic disease progression rates following treatment with sequential pembrolizumab and radiotherapy for locally advanced NSCLC with PD-L1 expression  $\geq 50\%$ .

**Hypothesis:** We hypothesize that sequential pembrolizumab and radiotherapy for locally advanced NSCLC with PD-L1 expression  $\geq 50\%$  prolongs freedom from intrathoracic disease progression compared to historical outcomes.

(3) **Objective:** To characterize overall survival rates following treatment with sequential pembrolizumab and radiotherapy for locally advanced NSCLC with PD-L1 expression  $\geq 50\%$ .

**Hypothesis:** We hypothesize that sequential pembrolizumab and radiotherapy for locally advanced NSCLC with PD-L1 expression  $\geq 50\%$  prolongs overall survival compared to historical outcomes.

(4) **Objective:** To estimate the rate of disease progression during 3 cycles of induction pembrolizumab prior to radiotherapy for locally advanced NSCLC with PD-L1 expression  $\geq 50\%$ .

**Hypothesis:** We hypothesize that the rate of disease progression during 3 cycles of induction pembrolizumab prior to radiotherapy for locally advanced NSCLC with PD-L1 expression  $\geq 50\%$  is less than 10%.

(5) **Objective:** To demonstrate, within the limitations of a nonrandomized study, that sequential pembrolizumab and radiotherapy for locally advanced NSCLC reduces severe adverse event rates compared to standard concurrent chemoradiotherapy.

**Hypothesis:** We hypothesize that sequential pembrolizumab and radiotherapy for locally advanced NSCLC reduces severe adverse event rates compared to standard concurrent chemoradiotherapy.

(6) **Objective:** To demonstrate, within the limitations of a nonrandomized study, that sequential pembrolizumab and radiotherapy for locally advanced NSCLC does not significantly increase rates of pneumonitis compared to standard concurrent chemoradiotherapy.

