## Target Volumes and Treatment Planning

Target lesions will be drawn on simulation CT imaging, using lung or mediastinal window levels as appropriate. PET imaging should be registered to simulation CT scans to aid with localization of hypermetabolic lesions. If 4D CT simulation is used, gross tumor volumes (GTVs) should be generated on each CT phase that will be used for treatment (typically 4/10 phases if respiratory gating is employed or 10/10 phases if the patient will be treated while breathing freely). GTVs will be combined to form internal target volumes (ITVs).

For patients treated with pembrolizumab and radiotherapy, the low-risk GTV (GTV\_4800) shall include the pulmonary tumor(s) as well as any suspicious lymph nodes (based on appearance, PET findings, size  $\geq$  1cm in short axis, or pathologic data). A high-risk gross tumor volume (GTV\_5500), will also be defined and will include only lesions with MTV  $>$  20 cc on PET obtained after induction pembrolizumab and before radiotherapy. MTV calculations will be performed on PET imaging using a semiautomatic gradient-based contouring algorithm (“PET Edge”, MIMvista Corp, Cleveland, OH) or using a thresholding tool to encompass all voxels with SUV  $>$  40% of the maximum SUV[46]. GTV\_5500 will be contained within GTV\_4800. Each GTV (or ITV) will be expanded by 7-10 mm to form a CTV (CTV\_4800 and CTV\_5500). CTVs may be trimmed to exclude anatomic boundaries to microscopic tumor spread. CTV\_5500 will be contained within CTV\_4800. Each CTV will be expanded to form a PTV. PTV expansions will be 5 mm in all directions if respiratory motion has been accounted for (e.g.: with beam gating, breath hold, or use of 4D-CT to form internal target volumes). Otherwise, PTV expansions will be 5 mm radially and approximately 10 mm in the superior and inferior directions. PTV\_5500 will be contained within PTV\_4800. Adaptive radiotherapy (adjustment of target volumes during the course of radiotherapy) is not allowed in this protocol, unless difficulties with daily patient setup require repeating the CT simulation procedure.

Subjects receiving standard concurrent chemoradiotherapy may be treated with a standard treatment planning approach, where the entire target volume is treated with a uniform prescription dose, or with a dose-painting technique. The prescription dose must be between 48 Gy and 66.6 Gy, delivered over a course of 20-37 fractions.

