## 8.0 STATISTICAL ANALYSIS PLAN

### 8.1 Statistical Analysis Plan – Primary Endpoint and Sample Size Calculation

The **primary endpoint** is progression-free survival (PFS) in the PembroRT cohort one year following study enrollment. PFS duration will be defined as the time from study registration to the date of disease progression or death from any cause. In cases where a scan is concerning for progressive disease based on RECIST 1.1 criteria, and progression is confirmed on a subsequent scan 4-8 weeks later (satisfying iRECIST criteria for progression), the date of disease progression would be the date of the first scan demonstrating progression. PFS rates will be estimated using the Kaplan-Meier Survival method, from which the probability of PFS at various time points and corresponding 95% confidence intervals will be estimated. If a patient is lost to follow-up without having disease progression, progression-free survival will be censored at the date of the patient's last clinic visit. Based on published multi-institutional trials and data from our institution, we expect the one-year progression-free survival rate ( $H_0$ ) to be to 40% with standard chemoradiotherapy. We hypothesize that this rate will be at least 65% ( $H_1$ ) for subjects in the PembroRT cohort. A one sample two-sided log-rank test will be used to compare the one-year PFS rate in the PembroRT cohort against the expected rate with ChemoRT. We plan to accrue **25 subjects to the PembroRT cohort**. Assuming that the accrual period will last 18 months and that event rates will follow an exponential distribution, this sample size will provide 81% power to detect an improvement in PFS at 1 year at a 5% level of significance using a one sample two-sided log-rank test [48, 49].

The ChemoRT cohort will be open to accrual while accrual to the PembroRT cohort is ongoing. We expect that approximately 40% of patients with locally advanced NSCLC have PD-L1 expression of at least 50%. We therefore expect that approximately 38 subjects will be enrolled and treated with standard concurrent chemoradiotherapy as part of this trial, which will yield a **total sample size of approximately 63 subjects**.

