#### *Resolution of iUPD*

Progression is considered not confirmed, and the overall response becomes iSD/iPR/iCR, if:

- None of the progression-confirming factors identified above occurs, AND
- The target lesion sum of diameters (initial target lesions) is not above the initial PD threshold.

The response is classified as iSD or iPR (depending on the sum of diameters of the target lesions), or iCR if all lesions resolve.

In this case, the initial iUPD is considered to be pseudo-progression, and the level of suspicion for progression is “reset”. This means that the next visit that shows radiographic progression, whenever it occurs, is again classified as iUPD by iRECIST, and the confirmation process is repeated before a response of iCPD can be assigned.

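### The plan does not say how progression first seen after induction is counted when radiotherapy comes before the confirmatory scan

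*Combined protocol and SAP*

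**What the plan says.** Four parts of the combined protocol and SAP bear on this.

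- **Section 8.1 (primary endpoint).** PFS runs from registration to progression or death. A scan suspicious by RECIST 1.1 gives its own date to the event under this condition: "progression is confirmed on a subsequent scan 4-8 weeks later (satisfying iRECIST criteria for progression), the date of disease progression would be the date". The section does not say what happens when the second scan fails to confirm.
- **Section 7.1.2.6.3.** RECIST 1.1 is the primary measure for response and for the date of progression. No confirming scan is mentioned.
- **Section 3.2, objective (4).** The aim is "To estimate the rate of disease progression during 3 cycles of induction pembrolizumab prior to radiotherapy", with a hypothesised rate below 10%. Section 8.2 reports this as counts and percentages and names no response criterion.
- **Appendix 4.** If no confirming factor occurs and the target sum is no longer above the progression threshold, the first reading is cancelled: "In this case, the initial iUPD is considered to be pseudo-progression, and the level of suspicion for progression is “reset". If no confirming factor occurs but the sum stays above the threshold, the reading remains unconfirmed (iUPD). No exception is made for local treatment given between the two scans.

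On treatment, the section on target volumes describes a PET taken between induction and radiotherapy. It defines a low-risk volume that "shall include the pulmonary tumor(s) as well as any suspicious lymph nodes". Sections 7.1.2.6 and 7.1.2.6.4, and the table on imaging and treatment after first progression, keep clinically stable patients on study treatment, or allow it, while confirmation is awaited.

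**The concern.** A confirming scan is meant to separate tumour flare on immunotherapy from true growth. That works if the treatment between the two scans is the one being judged. For a patient whose disease has grown on induction pembrolizumab, the treatment between the scans is definitive radiotherapy to the disease that grew. The second scan then largely shows the response to radiotherapy.

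Two results are exposed. Objective (4) measures the main risk of delaying radiotherapy, and lost events would push it towards the under-10% hypothesis. Primary PFS is tested against a fixed 40%, and lost events would push it towards the 65% hypothesis. The trial is open-label. With two definitions in the text, the choice between them could be made after the scans are known.

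**Working it through.** **1. The plan's own figure.** Inputs from Section 8.1: "25 subjects to the PembroRT cohort"; null one-year PFS "to be to 40% with standard chemoradiotherapy"; alternative "We hypothesize that this rate will be at least 65"%; "A one sample two-sided log-rank test will be used"; 5% level; 18 months' accrual; exponential times. Follow-up after the last entry is not stated.

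- Hazards: λ = −ln S(1), so λ0 = −ln 0.40 = 0.916 and λ1 = −ln 0.65 = 0.431 per year. The ratio is 0.470.
- Simulated power (100,000 trials, O observed and E expected events, |z| > 1.96): (O−E)/√E gives 80.6% with 10 months' follow-up after accrual, and (O−E)/√((O+E)/2) gives 80.5% with 6 months.

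The stated 81% can be reproduced and is not in dispute.

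**2. Timing.** The Section 6.0 header columns put induction in weeks 1–9 and radiotherapy from about week 10. The sequential alternative in Section 5.2.3 has 17 + 3 = 20 fractions. At an assumed five a week that is 4 weeks, so weeks 10–13. A post-induction scan at about weeks 8–10, plus 4–8 weeks, gives weeks 12–18. That runs from inside the radiotherapy course to about 5 weeks after it. The imaging rows of the flow chart cannot be read in the extracted text, so the scan weeks are approximate.

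**3. What Appendix 4 then does with intrathoracic progression.**

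- Irradiated lesions shrink, the target sum is no longer above the threshold, and nothing new appears: pseudo-progression, reset.
- Growth merely stops. Target-lesion confirmation needs a further increase of at least 5 mm, so with no other confirming factor and the sum still above the threshold the reading stays iUPD. The confirmation condition in Section 8.1 is not met.
- A new lesion appears, for instance outside the treated volume: confirmed.
- The patient is clinically unstable: no confirming scan is required.

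The first two routes can be produced by radiotherapy alone.

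**4. Size by counting.** One patient is 1/25 = 4 points. Since 10% of 25 is 2.5, an observed rate below 10% means at most 2 patients. Losing both would report 0/25 instead of 2/25 = 8%, and would raise one-year PFS by at most 8 points, reached only if both stay event-free to one year. The 10% line lies between 2/25 = 8% and 3/25 = 12%, so with 3 true progressors one reset is enough to make the hypothesis appear met. If the true rate were exactly 10%, the chance of 3 or more is 46%.

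**5. Size under the null.** The share with an event by week 9 is 1 − S(1)^(9/52). At 40% this is 14.7% (3.7 of 25), and at 65% it is 7.2% (1.8 of 25). These figures include deaths and distant progression, which radiotherapy cannot erase.

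Assume a share f of week 0–9 events is erased, that those patients restart at the same hazard from week 17, and that follow-up is 12 months after the last entry. Favourable-tail false-positive rates under the null (nominal 2.5%) are:

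| f (assumed) | One-year PFS | (O−E)/√E | (O−E)/√((O+E)/2) |
|---|---|---|---|
| 0% | 40% | 1.7% | 2.8% |
| 25% | 42% | 2.8% | 4.5% |
| 50% | 44% | 4.6% | 7.1% |
| 75% | 46% | 7.0% | 10.3% |
| 100% | 48% | 10.2% | 14.8% |

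The last row is an upper bound, because it also erases deaths and extrathoracic events.

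**The case against.** The strongest reply is that nothing is erased. Section 8.1 only dates progression that has been confirmed and does not call unconfirmed progression a non-event. Section 7.1.2.6.3 already makes RECIST 1.1 primary, iRECIST is used at the investigator's election, and no confirmation rule is attached to objective (4). All of this is correct. It shows that the harmful reading is one of two. It does not show which of them the analyst will follow, and Section 8.1 is where the primary endpoint is defined.

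A reader might go further and infer that induction progression can only be confirmed after radiotherapy and is therefore likely to be lost. The documents do not support that. They give no rate of reset. New extrathoracic lesions can still confirm, and unstable patients need no second scan. The sequence also needs radiotherapy to go ahead on schedule after a progression reading, which the text leaves partly to the investigator's discretion.

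Persistent iUPD could be offered as a further safeguard, since it is not a reset. It does not protect the endpoint: it is still unconfirmed, so on the Section 8.1 reading it need not count.

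**Conclusion.** The point holds as an unreconciled definition with a known direction of bias. If Section 8.1 is applied together with Appendix 4, true intrathoracic progression on induction can leave both PFS and objective (4) because radiotherapy came between the scans, and no text prevents this. If Section 7.1.2.6.3 is applied, the problem disappears.

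The size is 4 points per patient, and up to 8 points if induction progression is below 10% as hypothesised. The design difference is 25 points (65% − 40%). A reader might infer a shift of 12 points or more. That needs at least three lost events, all in patients who stay event-free to one year, and the documents give no basis for assuming it. The false-positive rates in the table depend wholly on the assumed f.

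The conclusion rests on radiotherapy proceeding on schedule and on scan weeks inferred from the flow chart header and the target-volume section. It does not challenge the 81% power figure. This is a cheap improvement.

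**What to change.** Add to Sections 8.1 and 8.2 only:

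- **Objective (4), in 8.2:** score progression by RECIST 1.1 on the post-induction, pre-radiotherapy scan against baseline, without confirmation. Name the scan that is read, because the target-volume section describes the PET only for planning.
- **PFS, in 8.1:** count RECIST 1.1 progression on that scan as an event on its date. For the analysis, a scan taken after radiotherapy has begun may not un-confirm it in irradiated lesions. State that this is consistent with Section 7.1.2.6.3.
- **Sensitivity analysis:** report PFS by the iRECIST-confirmed definition alongside.

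Leave Appendix 4 as it is. Its categories drive decisions to continue or stop treatment, so an edit there would reach beyond the analysis.

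The cost is a few sentences of analysis wording, with no new visits, provided the scan before radiotherapy can be read by RECIST 1.1. The downside is that an occasional true pseudo-progression during induction counts as progression, so the reported rates become slightly less favourable.

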### 8.2 Statistical Analysis Plan – Secondary Endpoints

Time-to-event outcomes (overall survival, freedom from distant metastasis, freedom from intrathoracic progression, freedom from hospitalization) will be analyzed using the Kaplan-Meier method, from which rates at various time points and corresponding 95% confidence intervals will be estimated. Exploratory comparisons for time-to-event outcomes between the PembroRT and ChemoRT cohorts will be performed using log-rank tests. Univariate and

multivariable Cox regression models will be used to evaluate associations between time-to-event outcomes and clinical covariates, including study cohort.

Rates of radiographic responses and disease progression during induction pembrolizumab for subjects in the PembroRT cohort will be described using counts and percentages. Logistic regression models will be used to evaluate potential predictors of response or progression (e.g.: PD-L1 TPS).

Hospitalization rates and adverse event rates, scored using CTCAE as well as PRO-CTCAE, will be presented as counts and percentages. Exploratory comparisons between the PembroRT cohort and the ChemoRT cohort will be performed using chi-square or Fisher Exact testing, as appropriate.

Daily step counts throughout the study period will be presented using descriptive statistics and will be analyzed using a generalized linear mixed-model for repeated measures.

Rates of circulating tumor DNA clearance will be presented as counts and percentages, and predictors of circulating tumor DNA clearance will be explored using chi-square or Fisher exact testing, as appropriate. Exploratory analyses will be performed to evaluate PD-L1 expression, expression of alternative immune checkpoint molecules (e.g., HHLA2, B7x, and B7-H3), baseline tumor mutational burden, and markers of immune activation (e.g., expansion of T4/T8 subsets, myeloid derived suppressor cell levels, expansion of T-cell repertoire) as predictors of PFS and overall survival.

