## 5.0 METHODOLOGY

### 5.1 Study Population

#### 5.1.1 Participant Inclusion Criteria

Participants are eligible to be included in the study only if all the following criteria apply:

1. Male/female participants who are at least 18 years of age on the day of signing informed consent with histologically confirmed diagnosis of non-small cell lung cancer will be enrolled in this study.
2. Previously untreated, pathologically proven NSCLC with measurable disease (at least 1 unidimensional, radiographically measurable lesion based on RECIST v1.1) and one of the following stages: (prior resection for early stage disease is allowed)
  - a. AJCC version 8 Stage II disease, medically or technically unresectable
  - b. AJCC version 8 Stage III disease
3. Whole body PET/CT within 42 days prior to study entry demonstrating hypermetabolic pulmonary lesion(s) and/or thoracic lymph node(s). If PET/CT was obtained more than 42 days prior to study entry and is not repeated, CT within 28 days prior to study entry demonstrating no evidence of metastatic disease is required.
4. MRI of the brain or head CT with contrast within 42 days prior to study entry.
5. PFTs within 42 days of study entry
6. ECOG performance status 0-1
7. Adequate end-organ function, based on routine clinical and laboratory workup:
  - a. ANC >1,500 cells/ $\mu$ l, Platelets  $\geq$  100,000 cells/ $\mu$ l, Hemoglobin  $\geq$  9.0 g/dl
  - b. Serum creatinine  $\leq$  1.5 x ULN or calculated creatinine clearance  $\geq$  50 ml/min
  - c. Total bilirubin  $\leq$  1.5 x ULN (or direct bilirubin below the ULN), AST and ALT  $\leq$  2.5 x ULN
  - d. International normalized ratio (INR) (or prothrombin time (PT)) and activated partial thromboplastin time (aPTT)  $\leq$  1.5 x ULN unless participant is receiving anticoagulant therapy, as long as values are within the intended therapeutic range

- e. Thyroid stimulating hormone (TSH) within normal limits. If TSH is not within normal limits, the participant may be eligible if T3 and free T4 are within normal limits.
8. A female participant is eligible to participate if she is not pregnant (see Exclusion Criteria), not breastfeeding, and at least one of the following conditions applies:
  - a. Not a woman of childbearing potential (WOCBP) as defined in the Appendix

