#### **7.1.2.6.3 RECIST 1.1 Assessment of Disease**

RECIST 1.1 will be used as the primary measure for assessment of tumor response, date of disease progression, and as a basis for all protocol guidelines related to disease status (e.g., discontinuation of study treatment). Although RECIST 1.1 references a maximum of 5 target lesions in total and 2 per organ, the Sponsor allows a maximum of 10 target lesions in total and 5 per organ, if clinically relevant to enable a broader sampling of tumor burden.

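### Predictors of response to induction are tested only on a yes/no response in at most 25 patients, although RECIST already yields a continuous measure of tumour change

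*Combined protocol and SAP*

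**What the plan says.** Section 8.2 has two sentences on induction. The first is descriptive: "Rates of radiographic responses and disease progression during induction pembrolizumab for subjects in the PembroRT cohort will be described using counts and percentages". The second is the model: "Logistic regression models will be used to evaluate potential predictors of response or progression (e.g.: PD-L1 TPS". Neither section 8.2 nor any other section plans an analysis of a continuous change in tumour size.

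The cohort is small. Section 8.1 plans "25 subjects to the PembroRT cohort", and only these patients receive induction.

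The continuous measure comes from the same assessments. Section 5.1.1 requires "at least 1 unidimensional, radiographically measurable lesion based on RECIST v1.1". Section 7.1.2.6.3 states that "RECIST 1.1 will be used as the primary measure for assessment of tumor response", and Appendix 4 classifies target lesions by their sum of diameters. Progression during induction is a secondary objective (section 3.2, objective 4), so disease has to be assessed at the end of induction. Section 5.2.3 (Target Volumes and Treatment Planning) also uses a PET "obtained after induction pembrolizumab and before radiotherapy", from which metabolic tumour volume (MTV) is calculated to define the high-risk target.

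**The concern.** For target lesions, response is a cut through the percent change in the sum of diameters. Patients just either side of the cut are treated as opposites, and patients far apart on the same side as identical. In 25 patients that discards information the trial can least spare. A real relation between a marker and tumour shrinkage is then more likely to be missed, and a null result for PD-L1 TPS could be read as evidence of no relation.

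RECIST categories are the right way to report a response rate. Nothing in RECIST requires the search for predictors to use the category as well.

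**Working it through.** **Inputs from the documents.** n = 25 (section 8.1). The outcome model is logistic (section 8.2). The two-sided 5% level is stated only for the primary test (section 8.1) and is carried over here as an assumption.

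**Inputs the documents do not give.** The response rate is assumed to be 20 to 60%, and the correlation between marker and tumour change 0.2 to 0.6.

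**The plan's own figure.** There is no power statement for the logistic models. The only power in the documents is 81% for the primary log-rank test. It reproduces as 80.6%, taking 18 months of accrual, an assumed 12 months of further follow-up and the expected-events variance. It has no bearing on section 8.2.

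**Step 1: information kept by a yes/no outcome.** If a normal outcome is cut so that a proportion p respond, the relative efficiency is φ(z_p)² / [p(1−p)].

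- p = 0.20: 0.2800² / 0.16 = 0.49, and 25 × 0.49 ≈ 12 patients
- p = 0.30: 0.3477² / 0.21 = 0.58, and 25 × 0.58 ≈ 14 patients
- p = 0.50: 0.3989² / 0.25 = 0.64, and 25 × 0.64 ≈ 16 patients

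So 25 patients carry the information of about 12 to 16. This step needs an assumed response rate but no correlation.

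**Step 2: power by simulation.** Marker and tumour change bivariate normal, n = 25, 30,000 data sets per cell. Linear regression on the change is compared with logistic regression (likelihood-ratio test) on the same change after the cut.

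| Correlation | Linear | Logistic at response rate 20 / 30 / 40 / 50% | Loss in points |
|---|---|---|---|
| 0.3 | 31% | 20.3 / 22.5 / 23.7 / 24.2% | 11.0 / 8.9 / 7.5 / 7.4 |
| 0.4 | 52–53% | 31.6 / 36.4 / 38.5 / 38.9% | 20.9 / 16.3 / 14.1 / 13.1 |
| 0.5 | 75% | 45.6 / 52.7 / 56.3 / 57.5% | 29.0 / 22.2 / 18.8 / 17.2 |
| 0.6 | 91% | 62.7 / 71.0 / 75.1 / 76.1% | 28.5 / 20.1 / 16.2 / 15.0 |

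With a uniform marker and response rates of 20 to 60%, the loss is about 2–3 points at correlation 0.2, 7–11 at 0.3, 13–21 at 0.4, 17–28 at 0.5 and 13–28 at 0.6. The likelihood-ratio test rejects in about 6–7% of data sets when there is no association, which slightly flatters the logistic model. With the Wald test (bivariate normal model, response rates 20–50%, correlations 0.3–0.6) the loss is 16–57 points.

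**Step 3: the rank-based version.** The fix uses Spearman correlation, which is slightly less efficient than linear regression when errors are normal: (3/π)² = 0.91, and 25 × 0.91 = 22.8 patients, against 12 to 16 for the cut. A check with the uniform marker (n = 25, 6,000 data sets per correlation, t approximation for the rank correlation) put Spearman about 5 to 25 points ahead of logistic regression where linear regression was about 7 to 28 ahead, and about 2 points ahead at correlation 0.2.

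**Step 4: effect of restricting TPS.** All PembroRT patients have TPS of 50% or higher (section 5.3). As an illustration, take TPS as uniform on 0–100% with a linear relation. Halving the range halves the standard deviation, so r becomes 0.5r / √(0.25r² + 1 − r²).

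- r = 0.4: 0.200 / √0.880 = 0.21
- r = 0.5: 0.250 / √0.8125 = 0.28

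In that range either analysis has only about 12–29% power, and the continuous one gains about 2–8 points.

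**The case against.** The strongest case is that the change buys little for the one marker named. With TPS cut off at 50%, correlations of 0.2 to 0.3 are plausible, and there neither analysis has useful power. This stands. It limits the benefit for TPS, but not for markers that are not truncated by the allocation rule.

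Logistic regression also matches the protocol's own response measure and gives an odds ratio that clinicians can read. RECIST response is not purely a cut of percent change either, since new and non-target lesions count (Appendix 4). Both points are fair. They are reasons to keep the categorical results, not to make them the only analysis.

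Four stronger readings are tempting, and the documents do not support them.

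- A reader might quote a single figure for lost power, such as 14 to 21 points. No response rate or correlation is stated, so any figure is conditional.
- A reader might infer that the PD-L1 objective rests on this model in 25 patients. Section 4.6.2.3 relates PD-L1 expression to outcomes, including PFS and overall survival, within each cohort, and section 8.2 repeats the PFS and survival analyses. The listed induction endpoint is progression, not response.
- A reader might infer that change in MTV is ready to use. MTV is planned only on the post-induction PET, by either of two contouring methods, and the baseline PET may be more than 42 days old if a CT is done (section 5.1.1, item 3).
- A reader might extend the point to progression. Progression can come from new or non-target lesions, which a change in target diameters does not capture, so the logistic analysis of progression is not challenged here.

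**Conclusion.** The point holds as a minor inefficiency. Section 8.2 tests predictors of induction response only on a dichotomised outcome in at most 25 patients, while a continuous outcome can be derived from the same RECIST measurements. Power was lost in every simulated scenario with a true association: about 7 to 28 points for correlations of 0.3 to 0.6 and response rates of 20 to 60%, and 2 to 3 points at a correlation of 0.2. These figures compare with linear regression, assume complete data in 25 patients and normal errors, and use the likelihood-ratio test. The Spearman version recovers most, not all, of the loss. No primary or decision-making analysis is affected.

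**What to change.** In section 8.2, make Spearman correlation between the continuous marker and the percent change in sum of target-lesion diameters, from baseline to the post-induction scan, the main analysis of predictors of response. Give the worst rank to patients with no post-induction scan because of progression or death, so that they are not dropped. Keep the RECIST response table, keep logistic regression on the response category as supportive, and leave the progression analysis as it is.

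If change in MTV is wanted, label it exploratory, measure baseline MTV by the same single method as the post-induction value, and analyse it by ranks. A log ratio is undefined when post-induction MTV is zero, which is the best outcome.

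The cost is a few sentences of SAP text and a little extra analysis. The diameter analysis needs no new scan; the MTV option needs an added baseline measurement. The downside is that percent change does not reflect new or non-target lesions, which is why the categorical table stays beside it.
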